10.6 Data Safety Plan

The PI of this Clinical Protocol will be responsible for the management of the protocol and data safety. Confidentiality of personal health information (PHI) will be maintained throughout the study. The investigators do realize that a risk to patient PHI confidentiality exists whereby personal information could accidentally be released, however, all necessary precautions will be taken to prevent this from happening. Unique patient identifiers will be used to replace patient name and medical record number. Patient identifiers will be available only to the investigators for the study and will be kept in a password-protected database and locked file cabinet. Paper records (data forms, list of patient names and unique identifiers, etc.) will be kept in a locked file cabinet with access granted only to study investigators. No identifying personal health information will be used in any publication from this study. Collected information (including patient identifiers) will be destroyed within 5 years after publication. The protected health information used in this study will not be reused or disclosed to any person or entity outside of the investigators nor will it be used for other research.

11.0 STATISTICAL CONSIDERATIONS

This will be a single arm, single center, open label study of lirilumab in combination with 5-azacytidine in patients with refractory, relapsed or untreated AML.

11.1 Sample Size

Part a. Lead-in phase

The primary objective of the lead-in phase is to determine the safety of lirilumab in combination with 5-azacytidine in patients with refractory/ relapsed AML. Up to 24 patients will be accrued into lead-in part of the study.

Part b. Phase II

Up to 40 patients (including 6 patients treated at the MTD from the lead-in part) will be recruited for the Phase II part.

The primary objective of the phase II is to determine the efficacy of lirilumab in combination with 5-azacytidine in patients with refractory, relapsed or untreated AML. The efficacy of the combination will be measured by the overall response rate (ORR), defined as CR (complete remission) + CRp (complete remission with incomplete platelet recovery) + CRi (complete remission with incomplete count recovery) + PR (partial response) + marrow clearance of blasts + HI (Hematological improvement) within 3 months of treatment initiation among adult patients with refractory/ relapsed AML. ORR and toxicity will be monitored simultaneously using the Bayesian approach of Thall, Simon, Estey (1995, 1996) and the extension by Thall and Sung (1998).

Once safety of the MTD has been established, any patients still on study at a dose lower than MTD can be dose escalated up to MTD. Patients treated in the lead-in phase at MTD will be included in the phase II portion of the study.

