5.2.1.1 The starting dose will be dose level -1.

Table 1. Dose levels of 5-azacytidine and lirilumab during the lead-in phase (part a)

Dose level	5-azacytidine (mg/m ² /d, Days 1-7)	Lirilumab (mg/kg, day 8)
-4	25	0.3
-3	50	0.3
-2	75	0.3
-1	75	1.0 (Starting dose)
0	75	3.0

5.2.1.2 The goal of the lead-in phase is to identify the dose at which <2/6 patients experience DLT. During the lead-in phase the dose’s of 5-azacytidine and lirilumab may be reduced if 2 or more patients experience DLT at any given dose. After the lead in phase the dose of lirilumab may not be reduced in the phase II portion of the study. For potential lirilumab related AEs in the phase II portion of the study only dose interruptions of lirilumab will be permitted. Dose reductions or escalations of 5-azacytidine will continue to be permitted in the phase II portion of the study and dose reductions or escalations of 5-azacytidine beyond those mentioned in table 5 or different to the doses specified should be discussed with the PI and documentation of the justification recorded in the chart.

5.2.1.3 The dose and /or schedule of administration is subject to modification pending information from ongoing clinical trials of lirilumab as a single agent and in combination with other drugs.

DLT is defined as clinically significant non-hematologic adverse event or abnormal laboratory value assessed as unrelated to disease progression, intercurrent illness, or concomitant medications and occurring during the first cycle on study that meets any of the following criteria:

- CTCAE Grade 3 AST (SGOT) or ALT (SGPT) for ≥ 7 days
- CTCAE Grade 4 AST (SGOT) or ALT (SGPT) of any duration
- All other clinically significant non-hematological adverse event that is Grade 3 or 4 according to the NCI common terminology criteria version 4.0 with the following exceptions:
 - Grade 3 or 4 nausea, vomiting and diarrhea will be considered DLT only if not controlled by optimal therapy.
 - Grade 3 biochemical abnormalities (e.g., lipase or bilirubin elevation) will only be considered DLT if accompanied by clinical consequences. Grade 3 or 4 electrolyte abnormalities will only be considered DLT if possibly related to study drug and not corrected by optimal replacement therapy.

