5.2.1.4 We will first treat 6 patients at dose level -1 in the lead-in phase. If DLT occurs in $\geq 2/6$ patients, this dose level would exceed the MTD, and 6 patients will be treated at the next lower dose level (i.e. dose level -2). If DLT is observed in the first 28 days of treatment in 0 or 1/6 at dose level -1, then dose level 0 will be evaluated. The dose adjustment (Table 1) will continue in cohorts of 6 until we reach a dose level at which $< 2/6$ patients experience a DLT in the first 28 days. The dose level at which 0-1/6 patients experience a DLT in the first 28 days of treatment will be the MTD and will be used to treat an additional 34 patients in the phase II portion of the study. If $\geq 2/6$ patients experience DLT at dose level -4, the study will be revised to consider additional lower dose levels (based on potential synergistic toxicity).

5.2.1.5 Patients that are removed from study before day 28 for any reason other than toxicity and have not experienced DLT will be replaced.

5.2.2 One cycle of therapy is defined as 28 days. Patients will receive one cycle of therapy every 28 days (+/- 7 days).

5.2.2.1 In the phase II part of the study (once the MTD dose has been defined) cycles may be started early (but not earlier than day 21) for patients with active disease if judged in the best interest of the patient.

For the lead-in cohort, DLT defining period is 28 days. As such, cycle 2 should not be started before 28 days for the patients being treated on the lead-in cohort.

5.2.2.2 Subsequent cycles may be delayed for recovery of toxicity or other medical conditions (e.g. infections). Delays in start of subsequent cycles greater than 8 weeks will be acceptable only for patients who are deriving clinical benefit and after discussion with the principal investigator of potential risk/benefit ratio.

5.2.2.3 In instances where one drug has to be discontinued transiently because of safety, the administration of the other drug may continue as scheduled. If the drug that is held can resume at a later time, no doses will be made up and the administration will follow the originally defined schedule calendar according to the drug that was continued.

5.2.2.4 Subsequent courses of 5-azacytidine and lirilumab may be administered regardless of peripheral blood counts during the first 4 cycles and/or in the presence of residual leukemia.

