11.2 Statistical Design

Part a. Lead-in phase

The MTD is defined as the highest dose level with ≤ 1 out of 6 patients experience a DLT during the first 28 days of treatment. DLT is defined in section 5.2.2. The dosing schema for the combination treatment during the lead in phase is shown in Table 1 in section 5.2.1.

Part b. Phase II

Historical data on similar patients shows an ORR of 10-15%. The target ORR with the experimental treatment is 30%. This regimen of the combination treatment will be considered worthy of further investigation if it elicits an increase in ORR to 30% with acceptable toxicity. A $>30\%$ drug-related grade 3/4 toxicity rate is considered unacceptable. Thus, interim monitoring rules, assuming the prior distributions above, were constructed that meet the following two conditions,

- 1) Stop if $\text{Prob}\{p(\text{ORR}, E) < p(\text{ORR}, H) + 0.15 \mid \text{data}\} > 0.975$, or
- 2) Stop if $\text{Prob}\{p(\text{TOX}, E) > 0.30 \mid \text{data}\} > 0.975$,

where $P(\text{ORR}, E)$ and $P(\text{TOX}, E)$ are the true ORR and toxicity rates for the combination treatment, and $p(\text{ORR}, H)$ is the true ORR rate of the standard treatment. The first rule provides for stopping the study if the data suggest that it is unlikely (i.e., probability $< 2.5\%$) that ORR rate of the combination treatment is greater than the ORR rate of standard treatment by 15.0%. The second condition will stop the study early if excessive therapy-related grade 3/4 toxicity ($>30\%$) is highly probable (i.e., probability $>97.5\%$) for the combination treatment. Monitoring for toxicity and futility will not begin until 5 patients have been evaluated, and cohort size for future evaluations is 5.

The monitoring rule for the toxicity rate, based on these assumptions and monitoring conditions above is found in Table 4. **For example, accrual will cease if 4 or more patients experience toxicities among the first 5 patients.**

Table 4. Stop accrual if the number of drug-related grade 3/4 toxicities is greater than or equal

to indicated (i.e., # patients with toxicities) among the number of patients evaluated								
# patients evaluated	5	10	15	20	25	30	35	40
# patients with toxicities	4-5	6-10	8-15	10-20	12-25	14-30	16-35	Always stop with this many patients

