Monitoring the ORR rate, based on the above assumptions and monitoring conditions is found in Table 5. **For example, accrual will cease if less than 2 patients experience an overall response within 3 months of initiation of therapy in the first 10 patients treated.**

Table 5. Stop accrual if the number with overall response is less than or equal to indicated (i.e., # patients with overall response) among the number of patients evaluated					
# patients evaluated	5	10-15	20-25	30-35	40
# patients with overall response	Never stop with this many patients	0-1	0-2	0-3	Always stop with this many patients

Multic Lean Desktop (version 2.1.0) was used to generate the toxicity and futility stopping boundaries and the OC table (Table 6). In order to utilize the software for the design, a beta (0.3, 1.7) and beta (0.4, 1.6) priors were assumed for the standard treatment response distribution and experimental treatment response prior distribution, respectively. In addition, a 30% toxicity constant rate and beta (0.6, 1.4) priors were assumed for the standard treatment toxicity constant rate and experimental treatment toxicity prior distribution, respectively.

The probability of stopping the study early if the true ORR of the combination treatment was 30% and the true toxicity rate was 30% was 15.1%. Probabilities of stopping early for high true toxicity rates (i.e., 50%) were 84.0% when the true ORR was 30% and 83.6% when true ORR rate was 40%.

Table 6. Operating characteristics for simultaneous monitoring response and toxicity rates for patients treated with combination treatment		
True Toxicity Rate	True ORR	Prob(stop the trial early)
0.10	0.15	0.3001
	0.20	0.1479
	0.25	0.0703
	0.30	0.0328

Table 6. Operating characteristics for simultaneous monitoring response and toxicity rates for patients treated with combination treatment

True Toxicity Rate	True ORR	Prob(stop the trial early)
	0.35	0.0151
	0.40	0.0069
0.20	0.15	0.3101
	0.20	0.1601
	0.25	0.0836
	0.30	0.0466
	0.35	0.0292
	0.40	0.0211
0.30	0.15	0.3859
	0.20	0.2523
	0.25	0.1842
	0.30	0.1514
	0.35	0.1358
	0.40	0.1286
0.40	0.15	0.6194
	0.20	0.5367
	0.20	0.4945
	0.30	0.4741
	0.35	0.4645
	0.40	0.4600
0.50	0.15	0.8841
	0.20	0.8589
	0.25	0.8460
	0.30	0.8398
	0.35	0.8369
	0.40	0.8355

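### The early-stopping probabilities in Table 6 treat all 40 phase II patients as unselected, although six are carried over only after passing the lead-in DLT limit, so the phase II toxicity figures are too high for a dose that has passed it

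*Combined protocol and SAP*

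**What the plan says.** Section 11.1 sets the phase II size: "Up to 40 patients (including 6 patients treated at the MTD from the lead-in part) will be recruited for the Phase II part". It adds: "Patients treated in the lead-in phase at MTD will be included in the phase II portion of the study". Section 5.2.1.4 gives the same split from the other side: the dose that passes "will be used to treat an additional 34 patients in the phase II portion of the study".

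Section 11.2 defines the MTD as the "highest dose level with ≤ 1 out of 6 patients experience a DLT" within 28 days. Section 5.2.1.3 begins its definition: "DLT is defined as clinically significant non-hematologic adverse event or abnormal laboratory value". It then limits DLTs to the first cycle and lists exceptions.

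The event monitored in phase II is wider. Section 11.2 says: "A $>30\%$ drug-related grade 3/4 toxicity rate is considered unacceptable". Table 4 counts drug-related grade 3/4 toxicities at 5, 10, 15, 20, 25, 30 and 35 patients. Table 6 gives the probability of stopping early. The text beside it quotes 15.1% at 30% toxicity and 30% ORR. For 50% toxicity it says that the probabilities "were 84.0% when the true ORR was 30" per cent, and 83.6% when it was 40%.

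No sentence removes the six from the Table 4 looks, and none says that Table 6 allows for the lead-in rule.

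**The concern.** A stopping probability computed for unselected patients does not describe a sequence whose first six members were kept because they had few events. Had that cohort shown two or more DLTs, its dose level would not be the phase II dose. As far as the monitored toxicities are also DLTs, the running count starts artificially low and the Table 4 boundaries are harder to reach.

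This matters where the phase II rule is most needed, namely when a too-toxic dose has passed the lead-in by chance. The quoted percentages are the plan's evidence that the rule would then act. The same selection lowers the pooled toxicity estimate, because section 11.2 analyses safety in everyone who received any study drug.

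**Working it through.** **Inputs from the documents.** 40 patients = 6 carried over + 34 new (sections 11.1 and 5.2.1.4). Lead-in limit: at most 1 DLT in 6. Table 4 toxicity boundaries: stop at 4/5, 6/10, 8/15, 10/20, 12/25, 14/30, 16/35. Table 6 as printed.

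**Assumptions not in the documents.** A share s of monitored toxicities are DLTs, with s = 100%, 75%, 50% or 25%. Patients are independent, and so are toxicity and response. The six occupy the first six places in the looks.

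**Step 1: reproduce Table 6.** An exact patient-by-patient binomial recursion gives T, the probability of never crossing the toxicity boundary, and R, the probability of never crossing the response boundary. Then P(stop) = 1 − T × R. Response cut-offs of ≤0 at 10–15, ≤1 at 20–25 and ≤2 at 30–35 give R = 0.9677 at ORR 30%:

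- Toxicity 50%: T = 1 − 0.8345 = 0.1655; 1 − 0.1655 × 0.9677 = 0.8398 (Table 6: 0.8398).
- Toxicity 40%: T = 1 − 0.4566 = 0.5434; 1 − 0.5434 × 0.9677 = 0.4741 (Table 6: 0.4741).
- Toxicity 30%: T = 1 − 0.1231 = 0.8769; 1 − 0.8769 × 0.9677 = 0.1514 (Table 6: 0.1514).

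All 30 cells match within 0.00005, with every patient unselected. These response cut-offs are one below those printed in Table 5. With Table 5 as printed, the 50%/30% cell would be 0.8605. That mismatch is a separate matter, and the toxicity component (83.5% at 50%) does not depend on it.

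**Step 2: probability of passing the lead-in.** With q = toxicity rate × s, P(pass) = (1 − q)^6 + 6q(1 − q)^5. At 50% toxicity:

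- s = 100%: q = 0.5, P(pass) = 7/64 = 0.1094.
- s = 25%: q = 0.125, P(pass) = 0.8335.

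**Step 3: stopping probability given a pass, ORR 30%.** This is the same recursion restricted to paths with at most 1 DLT among the first six.

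| True toxicity | Table 6 | s = 100% | 75% | 50% | 25% |
|---|---|---|---|---|---|
| 50% | 84.0% | 55.2% | 69.6% | 77.7% | 82.3% |
| 40% | 47.4% | 19.5% | 29.8% | 38.5% | 44.7% |
| 30% | 15.1% | 5.2% | 7.7% | 10.8% | 13.7% |

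**Step 4: lead-in and phase II combined.** P(fail lead-in or stop in phase II) = 1 − P(pass) × [1 − P(stop given pass)]. At 50% toxicity and ORR 30%:

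- s = 100%: 1 − 0.1094 × (1 − 0.5517) = 0.951.
- s = 25%: 1 − 0.8335 × (1 − 0.8225) = 0.852.

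**Step 5: if the six do not count.** Looks at 5 to 30 in the 34 new patients give toxicity-only stopping of 79.3% at 50% toxicity, against 83.5% in Table 6's own setting. With the response rule the figure is about 80.0%.

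**Step 6: pooled toxicity rate over 40 patients.** At full overlap and 50% toxicity, the expected count in the six is (6/64)/(7/64) = 0.857 instead of 3, so the bias is (3 − 0.857)/40 = 5.4 points downward. At 30% it is (1.8 − 0.72)/40 = 2.7 points. At half overlap the biases are 1.4 and 0.8 points; at quarter overlap, 0.4 and 0.2.

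**The case against.** **Full overlap is not realistic.** DLTs are non-hematologic, confined to cycle 1 and subject to exceptions. Table 4 counts drug-related grade 3/4 toxicity with no organ or time limit, and section 5.4.1 plans up to 24 cycles. A carried-over patient can therefore have an event that counts in Table 4 but did not count in the lead-in. This stands. A reader might infer that the true figure is 55.2% rather than 84.0%, or that the looks at 5 and 10 cannot fire. Both hold only if every monitored toxicity is a DLT: then at most 1 event is possible at 5 patients, and at most 1 + 4 = 5 at 10 against a boundary of 6. At half overlap and 50% toxicity, the look at 10 still stops 17.5% of trials that passed the lead-in.

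**The lead-in is itself a toxicity stop.** A reader might infer that the trial as a whole protects patients less than stated. The figures do not support that: the combined probability at 50% toxicity exceeds 84.0% at every share examined. The selection effect is also largest where passing is least likely (10.9% at full overlap). This stands, but it concerns a different quantity. The text presents 84.0% as the probability of stopping under the phase II rules, and that figure is neither the conditional nor the combined one.

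**Inclusion of the six at the looks is inferred.** This is correct, but leaving them out does not restore 84.0% (about 80.0%).

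**Table 6 has no arithmetic error.** This is also correct. It is a conventional unconditional table; what is missing is the conditioning that the design imposes.

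**Conclusion.** The point holds in a limited form. Once a dose has passed the lead-in, and if the six count at the Table 4 looks, Table 6 overstates the probability that phase II monitoring stops for toxicity. At ORR 30% the overstatement is 28.8 points (84.0 − 55.2) down to 1.7 points (84.0 − 82.3) at 50% toxicity; 27.9 to 2.7 points at 40%; and 9.9 to 1.4 points at 30%. The direction is the same at every share examined. The size rests on the overlap between DLTs and monitored toxicities, which the documents do not give, and the upper end is a bound. The downward bias in the pooled toxicity rate is likewise small unless overlap is high. The documents do not support a claim that the overall safety protection of lead-in plus phase II is overstated.

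**What to change.** 1. State in section 11.1 or 11.2 whether the six carried-over patients count at the Table 4 looks.
2. Recompute Table 6 and the three quoted probabilities conditional on passing the lead-in, over a stated range of overlap between DLTs and monitored toxicities. Give the combined lead-in plus phase II probability alongside, and name the response cut-offs used, since those that reproduce Table 6 differ from Table 5.
3. Report the drug-related grade 3/4 toxicity rate in the 34 new patients beside the pooled rate.

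Table 4 should not also be run as a second stopping rule on the 34. That would change the design and would need its own joint operating characteristics.

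The cost is a recalculation, one extra line of reporting, and phase II stopping figures that look less favourable. No patients are added.

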11.2 Statistical Design

Part a. Lead-in phase

The MTD is defined as the highest dose level with ≤ 1 out of 6 patients experience a DLT during the first 28 days of treatment. DLT is defined in section 5.2.2. The dosing schema for the combination treatment during the lead in phase is shown in Table 1 in section 5.2.1.

Part b. Phase II

Historical data on similar patients shows an ORR of 10-15%. The target ORR with the experimental treatment is 30%. This regimen of the combination treatment will be considered worthy of further investigation if it elicits an increase in ORR to 30% with acceptable toxicity. A $>30\%$ drug-related grade 3/4 toxicity rate is considered unacceptable. Thus, interim monitoring rules, assuming the prior distributions above, were constructed that meet the following two conditions,

- 1) Stop if $\text{Prob}\{p(\text{ORR}, E) < p(\text{ORR}, H) + 0.15 \mid \text{data}\} > 0.975$, or
- 2) Stop if $\text{Prob}\{p(\text{TOX}, E) > 0.30 \mid \text{data}\} > 0.975$,

where $P(\text{ORR}, E)$ and $P(\text{TOX}, E)$ are the true ORR and toxicity rates for the combination treatment, and $p(\text{ORR}, H)$ is the true ORR rate of the standard treatment. The first rule provides for stopping the study if the data suggest that it is unlikely (i.e., probability $< 2.5\%$) that ORR rate of the combination treatment is greater than the ORR rate of standard treatment by 15.0%. The second condition will stop the study early if excessive therapy-related grade 3/4 toxicity ($>30\%$) is highly probable (i.e., probability $>97.5\%$) for the combination treatment. Monitoring for toxicity and futility will not begin until 5 patients have been evaluated, and cohort size for future evaluations is 5.

The monitoring rule for the toxicity rate, based on these assumptions and monitoring conditions above is found in Table 4. **For example, accrual will cease if 4 or more patients experience toxicities among the first 5 patients.**

Table 4. Stop accrual if the number of drug-related grade 3/4 toxicities is greater than or equal

to indicated (i.e., # patients with toxicities) among the number of patients evaluated								
# patients evaluated	5	10	15	20	25	30	35	40
# patients with toxicities	4-5	6-10	8-15	10-20	12-25	14-30	16-35	Always stop with this many patients

Monitoring the ORR rate, based on the above assumptions and monitoring conditions is found in Table 5. **For example, accrual will cease if less than 2 patients experience an overall response within 3 months of initiation of therapy in the first 10 patients treated.**

Table 5. Stop accrual if the number with overall response is less than or equal to indicated (i.e., # patients with overall response) among the number of patients evaluated					
# patients evaluated	5	10-15	20-25	30-35	40
# patients with overall response	Never stop with this many patients	0-1	0-2	0-3	Always stop with this many patients

Multic Lean Desktop (version 2.1.0) was used to generate the toxicity and futility stopping boundaries and the OC table (Table 6). In order to utilize the software for the design, a beta (0.3, 1.7) and beta (0.4, 1.6) priors were assumed for the standard treatment response distribution and experimental treatment response prior distribution, respectively. In addition, a 30% toxicity constant rate and beta (0.6, 1.4) priors were assumed for the standard treatment toxicity constant rate and experimental treatment toxicity prior distribution, respectively.

The probability of stopping the study early if the true ORR of the combination treatment was 30% and the true toxicity rate was 30% was 15.1%. Probabilities of stopping early for high true toxicity rates (i.e., 50%) were 84.0% when the true ORR was 30% and 83.6% when true ORR rate was 40%.

Table 6. Operating characteristics for simultaneous monitoring response and toxicity rates for patients treated with combination treatment		
True Toxicity Rate	True ORR	Prob(stop the trial early)
0.10	0.15	0.3001
	0.20	0.1479
	0.25	0.0703
	0.30	0.0328

Table 6. Operating characteristics for simultaneous monitoring response and toxicity rates for patients treated with combination treatment

True Toxicity Rate	True ORR	Prob(stop the trial early)
	0.35	0.0151
	0.40	0.0069
0.20	0.15	0.3101
	0.20	0.1601
	0.25	0.0836
	0.30	0.0466
	0.35	0.0292
	0.40	0.0211
0.30	0.15	0.3859
	0.20	0.2523
	0.25	0.1842
	0.30	0.1514
	0.35	0.1358
	0.40	0.1286
0.40	0.15	0.6194
	0.20	0.5367
	0.20	0.4945
	0.30	0.4741
	0.35	0.4645
	0.40	0.4600
0.50	0.15	0.8841
	0.20	0.8589
	0.25	0.8460
	0.30	0.8398
	0.35	0.8369
	0.40	0.8355

All patients who received any dose of the study agent will be included in the analysis for efficacy and safety. Demographic/clinical characteristics (including duration of response) and safety data of the patients will be summarized using descriptive statistics such as mean, standard deviation, median and range. For the primary efficacy analysis, we will estimate the ORR for the combination treatment, along with the 95% confidence interval. Patients who drop out of the study before completing all the cycles will be treated as “failures” for the primary analysis. ORR during the study period will also be presented with the 95% confidence interval. The association between ORR and patient’s clinical characteristics will be examined by Wilcoxon’s rank sum test or Fisher’s exact test, as appropriate. Toxicity type, severity and attribution will be summarized for each patient using frequency tables.

The distribution of time-to-event endpoints (DFS and OS) including overall survival and progression free survival will be estimated using the method of Kaplan and Meier. Comparisons of time-to-event endpoints by important subgroups will be made using the log-rank tests. Paired t-tests will be used to determine the immunological and molecular changes in the peripheral blood and bone marrow from baseline to the time of response, and to the time of disease progression. Correlation analysis (such as logistic regression analysis) will be conducted to determine the relationship between induction of hypomethylation / DNA damage and clinical response.

Statistical analysis of biomarker data: Descriptive statistics including plots, mean, median and standard deviations will be used to summarize data. For continuous outcomes, t-test and ANOVA will be used to compare outcome measures across patient characteristics. Dunnett’s and Tukey’s test that properly adjust for multiplicity in multiple tests will be implemented. Pair-wise comparisons will be performed using pre- and post-therapy samples from each patient . The chi-square test or Fisher’s exact test will be used to test the association between two categorical variables such as disease state and performance status. Both univariate and multivariate logistic regressions will be performed to model prognostic factors.

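### Phase II "acceptable toxicity" has no end-of-trial test: completing without a Table 4 stop does not show a rate of 30% or less, and Table 4 does not match the stated 0.975 cut-off

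*Combined protocol and SAP*

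**What the plan says.** Section 11.2, Part b, sets a two-part condition for the phase II conclusion: the combination "will be considered worthy of further investigation if it elicits an increase in ORR to 30% with acceptable toxicity". The limit on the safety half follows at once, since a rate above 30% is ruled out: "drug-related grade 3/4 toxicity rate is considered unacceptable".

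Rule 2 stops the study when the posterior probability that toxicity exceeds 0.30 is above 0.975. The text explains that this happens when excess toxicity "is highly probable (i.e., probability $>97.5\%$) for the combination treatment". For the calculation, "a 30% toxicity constant rate and beta (0.6, 1.4) priors were assumed". Table 4 turns the rule into counts at 5, 10, ..., 35 patients: 4, 6, 8, 10, 12, 14 and 16 or more. At 40 patients it gives no count, only "Always stop with this many patients".

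The analysis paragraph of 11.2 gives ORR a 95% confidence interval. For toxicity it says: "Toxicity type, severity and attribution will be summarized for each patient using frequency tables". On operating characteristics, the text above Table 6 gives 15.1% early stopping at 30% toxicity with 30% ORR, and then: "Probabilities of stopping early for high true toxicity rates (i.e., 50%) were 84.0% when the true ORR was 30"%. The 40% toxicity rows are in Table 6 but not in the prose.

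**The concern.** A stopping rule that needs strong evidence of harm is a reasonable interim safeguard, but it answers a different question from the one in the conclusion. Not crossing it means that an excess over 30% was not shown with high probability. It does not mean that the rate is 30% or less. Since the final analysis has no interval, posterior probability or limit for toxicity, a trial that reaches 40 patients has no written way to settle the safety half of its own condition.

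At stake is a judgement that the regimen is acceptably safe at a rate the plan itself calls unacceptable. Section 2.6 foresees moving to the frontline setting if the combination is well tolerated and improves response, and the plan gives no numeric meaning to well tolerated beyond this limit.

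The written cut-off and the printed counts also need to agree, because the operating characteristics depend on which of them is applied.

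**Working it through.** **Inputs (all from 11.2).** Limit 0.30; prior Beta(0.6, 1.4) for experimental toxicity; looks every 5 patients from 5 to 35; maximum 40; Table 4 counts as above.

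**Step 1. Reproduce Table 6.** Let S(p) be the probability of passing all toxicity looks at true rate p, from an exact recursion: add Binomial(5, p) at each look and remove paths at or above the Table 4 count. Let R(q) be the same for the response rule at true ORR q. With toxicity and response independent, P(stop early) = 1 − S(p) × R(q).

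- Toxicity 0.40, ORR 0.30: 1 − 0.5434 × 0.9677 = 0.4741 (Table 6: 0.4741).
- Toxicity 0.40, ORR 0.40: 1 − 0.5434 × 0.9937 = 0.4600 (Table 6: 0.4600).
- Toxicity 0.50, ORR 0.30: 1 − 0.1655 × 0.9677 = 0.8398 (Table 6: 0.8398).

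All 30 cells reproduce to within 0.00005, reading the second row labelled 0.20 in the 40% block as ORR 0.25. This uses Table 4 as printed and response limits of 0/10, 0/15, 1/20, 1/25, 2/30 and 2/35 or fewer, which are one lower than printed Table 5. With Table 5 as printed, completion at 40% toxicity is 0.5434 × 0.8431 = 45.8% at ORR 0.30 and 0.5434 × 0.9529 = 51.8% at ORR 0.40.

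**Step 2. What a completed trial can look like.** The most toxicities that can be reached without a stop are 15 at 35 patients plus 5 more, so 20/40 (50%), with an exact 95% interval of 33.8% to 66.2%. At a true rate of 40%, 54.3% of trials complete on the toxicity rule alone, and 41.9% of all trials complete with more than 12/40. That is 0.4194 / 0.5434 = 77% of those that complete.

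**Step 3. Table 4 against rule 2.** After x toxicities in n patients, the posterior is Beta(0.6 + x, 1.4 + n − x).

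| Table 4 limit | P(TOX > 0.30) at the limit | With one more toxicity |
|---|---|---|
| 4/5 | 0.975 | 0.998 |
| 6/10 | 0.962 | 0.991 |
| 8/15 | 0.960 | 0.988 |
| 10/20 | 0.961 | 0.986 |
| 12/25 | 0.963 | 0.986 |
| 14/30 | 0.967 | 0.986 |
| 16/35 | 0.970 | 0.987 |

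Only the first look meets 0.975. Applied literally, rule 2 gives 4/5, 7/10, 9/15, 11/20, 13/25, 15/30 and 17/35, and 69.1% of trials would then complete at 40% toxicity.

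**Step 4. Effect of a final criterion.** At n = 40 the posterior P(TOX > 0.30) is 0.482 at 12, 0.615 at 13, 0.973 at 18, 0.988 at 19 and 0.995 at 20. A posterior below 0.5 therefore means at most 12/40. With printed Table 4 in place:

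| True toxicity | Completes without a stop | Completes with at most 12/40 |
|---|---|---|
| 10% | 0.999 | 0.999 |
| 20% | 0.985 | 0.948 |
| 25% | 0.953 | 0.807 |
| 30% | 0.877 | 0.563 |
| 35% | 0.738 | 0.305 |
| 40% | 0.543 | 0.124 |
| 50% | 0.166 | 0.008 |

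Extending rule 2 to 40 patients at 0.975 (19 or more fails) would change little: the pass probability at 40% toxicity goes from 0.543 to 0.537.

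**The case against.** Table 4 governs accrual, and at 40 patients accrual is over. Table 5 has the same entry there. An interim boundary was never meant to certify safety, and Table 6 openly prints the 40% rows. The 30% limit is also written down, so a reader could compare 20/40 in the frequency tables with it. The lead-in requires 0-1 DLTs in 6 patients, section 9.2 allows a discretionary safety stop, and section 2.6 makes frontline use conditional on tolerability.

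Much of this stands, and it rules out some stronger readings.

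- A reader might infer that the empty 40-patient entry causes the 54%. It does not: completion means passing the looks at 5 to 35, and a limit at 40 changes only the final verdict.
- A reader might attribute the 54% to a 97.5% requirement. It comes from the printed counts, which from 10 patients on are less strict about proof than 0.975.
- A reader might infer that the weakness is concealed or miscalculated. Table 6 shows it, and its figures reproduce.
- A reader might infer that nothing else screens toxicity. The lead-in gate and section 9.2 do, but the first uses a cycle 1 non-hematologic endpoint and the second has no number.

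The objection does not supply a rule for judging toxicity at the end. A bare 30% limit does not say whether the observed rate, an interval or a posterior probability is to be compared with it. A firm cut also needs a clean numerator. Section 11.2 does not say whether grade 3/4 myelosuppression counts or over what period, while section 10.2 records only unexpected events in the CRF and lists cytopenias as expected.

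**Conclusion.** The point holds as a missing final criterion together with a mismatch between text and table. The plan conditions its conclusion on toxicity of 30% or less but tests this only with an early-stopping rule, so a completing trial has no safety verdict. At a true rate of 40%, completion is 54.3% on the toxicity rule alone and 52.6% at ORR 0.30 by Table 6, and 41.9% of all such trials complete with an observed rate above 30%. Separately, rule 2 and Table 4 disagree at every look from 10 patients on.

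The figures assume the printed Table 4 counts, looks at exactly 5 to 35 patients, a constant toxicity rate, and independence of toxicity and response where both rules are combined. The combined figure depends on the response limits behind Table 6, and is 45.8% at ORR 0.30 with Table 5 as printed. The conclusion does not change across this range. It is worth correcting before the final analysis, but it does not invalidate interim monitoring.

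**What to change.** In section 11.2:

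1. Reconcile rule 2 with Table 4, so that the stated cut-off, prior and printed counts agree, and recompute Table 6 if the counts change. Keep interim monitoring after that.
2. State that not crossing Table 4 does not establish acceptable toxicity.
3. At the end of the trial, report the monitored toxicity rate with its 95% interval and P(TOX > 0.30 | data).
4. Pre-specify how these are judged against the plan's own 30% limit. A posterior below 0.5, meaning at most 12/40, is one example. Other cut-offs are possible, and the choice is the sponsor's.
5. Give the operating characteristics of the chosen criterion, including true rates of 20%, 25% and 30%.
6. Define which grade 3/4 events count and over what period, and make sure they are captured.

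The cost is some text, one posterior calculation, and possibly wider event capture under item 6. No more patients are needed. The downside is more failures for regimens at or below the limit: with the example criterion and printed Table 4, the pass probability falls from 0.985 to 0.948 at 20% toxicity, from 0.953 to 0.807 at 25% and from 0.877 to 0.563 at 30%. In return it falls from 0.543 to 0.124 at 40% and from 0.166 to 0.008 at 50%.
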